Appendix D. Clinical Trial Pharmacovigilance Investigator Guide

Introduction

The purpose of this document is to provide relevant background information and proposed criteria to determine whether an adverse event (AE) or serious adverse event (SAE) should be attributed to the VTL C3A cells (biologic), the ELAD System (device), or to the ELAD Procedure.

ELAD-Related Adverse Events

VTL C3A Cells in ELAD Cartridges: Overview

The active drug product within the ELAD C3A cell cartridge are the VTL C3A cells, which are derived from a subclone of the human hepatoblastoma cell line HepG2. VTL C3A cells are monitored during the manufacturing process for the production of liver-specific proteins (e.g., albumin and transferrin) and for cell viability (oxygen utilization and glucose consumption). Oxygen utilization and glucose consumption by the VTL C3A cells are monitored closely during the course of patient treatment.

The 0.2- μ m hollow-fiber membrane that physically separates the VTL C3A cells from the patient ultrafiltrate allows diffusion of inflammatory cytokines, toxins, system source oxygen and system source glucose towards the VTL C3A cells and the simultaneous delivery of secreted macromolecules and other cellular products into the patient's ultrafiltrate.

Hepatocyte functions used to assess VTL C3A cell function include: α -fetoprotein, albumin, factor V, monoethylglycine-xyliide (surrogate marker of cytochrome P450 enzyme activity), transferrin, transforming growth factor- α , and urea production; galactose and glucose consumption; oxygen utilization rate; and lactate production to glucose consumption ratio are displayed in the Investigator's Brochure. Post-treatment ELAD cartridges maintained viability, made liver specific proteins, and metabolized galactose and lidocaine at levels similar to pre-treatment ELAD cartridges containing VTL C3A cells released from manufacturing (see Investigator's Brochure).

The in-line cell filter (0.2- μ m hollow fiber filter) prevents any VTL C3A cells that may have escaped from the ELAD cartridges from passing into subjects. Histological examination of a sample of ELAD cartridges revealed no broken fibers (>50,000 observations).

Adverse Events: VTL C3A Cells (Biologic)

Adverse events (AEs) or SAEs that may be attributed to VTL C3A cells should be considered when there appears to be clinically-significant changes in hepatic function (synthesis, conjugation, and secretion) or allergic reactions while a subject is undergoing ELAD treatment.

The following point should be noted when assessing changes in hepatic function while subjects are on ELAD treatment:

- Increased levels of α -fetoprotein have been observed in ELAD-treated subjects in prior studies and are considered to be a surrogate marker of exposure of the plasma ultrafiltrate to VTL C3A cells. Levels of up to approximately 10×10^7 ng/dL have been reported while subjects are on ELAD.

Expected Adverse Events: VTL C3A Cells¹ (Biologic)

Based on a review of safety data from past clinical studies and investigator assessments of AEs in the VTI-208 study, the following AEs could potentially be related to VTL C3A cell function:

Acidosis	Coagulopathy	Hypersensitivity	Lactic acidosis
Alkalosis	Device occlusion	Hypoglycemia	Metabolic acidosis
Allergic reaction	Fungal infection	Hypotension	Pyrexia
Anaphylactic reaction	Hemolysis	Increased ammonia levels	Rash maculopapular
Cartridge malfunction	Hepatic enzyme increased	Increased AST, ALT, and LDH levels	Thrombocytopenia

¹ Listed alphabetically

ELAD System (Device)

ELAD System: Overview

The current ELAD System, depicted in the [Investigator's Brochure](#), first draws blood from the subject via a dual-lumen catheter placed in a large vein using an extracorporeal pumping unit, and then separates the plasma fluid (ultrafiltrate) from cellular components by using a specifically-designed ultrafiltrate generator cartridge. While the cellular components are returned to the subject via the venous access, the ultrafiltrate is circulated at a high-flow rate through four metabolically-active ELAD cartridges.

The cartridge that houses the VTL C3A cells contains approximately eight thousand hollow fibers made up of a semi-permeable polysulfone material that has a nominal pore size of 0.2- μ m ([Brotherton 2007](#)). During ELAD treatment, an extracorporeal pumping system pumps the subject's ultrafiltrate through the hollow fibers of the cartridge wherein the semipermeable membrane permits a bidirectional flow between the cells (grown between the hollow fibers) and the ultrafiltrate (contained in the lumen of the hollow fibers). Toxins, nutrients and dissolved oxygen pass from the ultrafiltrate to the cells, while the potentially-beneficial macromolecules and other substances synthesized by the cells simultaneously pass into the patient's ultrafiltrate.

After circulation through the cartridges, the ultrafiltrate passes through a 0.2- μ m pore size filter, is recombined with the cellular components of the subject's blood, and is returned to the patient through the dual-lumen catheter. The toxins metabolized by the VTL C3A cells are thereby returned to the subject to be excreted by the renal or gastrointestinal system. This circulation is maintained continuously for the duration of ELAD treatment, typically between three and five days.

Adverse Events: ELAD System (Device)

Adverse events should be attributed to the ELAD System when malfunctions of the bedside unit or contamination of catheters, tubing sets or filter components arise while the subject is undergoing ELAD treatment.

Expected Adverse Events: ELAD System¹ (Device)

Based on a review of safety data from past clinical studies and investigator assessments of AEs in the VTI-208 study, the following AEs could potentially be related to the ELAD System:

Abdominal infection	Coagulopathy	Hypocalcaemia	Pyrexia
Activated partial thromboplastin time prolonged	Catheter site haemorrhage	Hypofibrinogenaemia	Rectal haemorrhage
Air embolism	Disseminated intravascular coagulation	Hypotension	Thrombocytopenia
Allergic reaction	Haemorrhage	Hypothermia	
Anemia	Hemolytic anaemia	Infection	
Anaphylactic reaction	Hypersensitivity	Lung Infection	

¹ Listed alphabetically

Abdominal distension	Device related sepsis	Hypernatraemia	Multi-organ failure
Acute respiratory distress syndrome	Disseminated intravascular coagulation	Hypersensitivity	Oedema peripheral
Agitation	Ecchymosis	Hypertension	Oliguria
Allergic reaction	Edema	Hypocalcemia	Pain
Anaemia	Edema peripheral	Hypocoagulable state	Pneumonia
Anuria	Electrolyte imbalance	Hypofibrinogemaemia	Pulmonary oedema
Application site bleeding	Encephalopathy	Hypokalaemia	Renal failure acute
Ascites	Epistaxis	Hypomagnesaemia	Respiratory arrest
Asthma	Fever	Hypophosphataemia	Tachycardia
Atrial fibrillation	Fluid overload	Hypotension	Thrombocytopenia
Bacteremia	Gastrointestinal haemorrhage	Hyothermia	Vessel puncture site haematoma
Blood lactate dehydrogenase (LDH) increased	Gingival bleeding	Hypovolemia	Wound secretion
Blood pressure decreased	Haematemesis	Ileus	
Catheter site hematoma	Haematuria	Infection	
Catheter site hemorrhage	Hemoglobin decreased	Injection site haemorrhage	
Catheter site pain	Hemolysis	Ischemic hepatitis	
Catheter site reaction	Haemorrhage	Leukocytosis	
Coagulation disorder	Hepatic encephalopathy	Melaena	
Coagulation prolonged	Hepatic failure	Mental status changes	

¹ Listed alphabetically

Expected Adverse Events: Extracorporeal Procedures

Certain adverse events are typically observed in patients undergoing treatment with extracorporeal procedures. Anemia, coagulopathy, and thrombocytopenia tend to be the most common adverse events observed during treatment with extracorporeal procedures. Specific details about each of these adverse events are presented in the following sections.

Anemia

Data from prior ELAD clinical studies (PS-0698; CR-202, VTIC-301, VTI-201, VTI-206 and VTI-208) indicate that hemoglobin levels tend to decrease after ELAD treatment is started. The reduced hemoglobin levels may be related to mechanical hemolysis, which is occasionally observed in patients undergoing other extracorporeal procedures (Boehning 2014). Patients with chronic liver disease may be predisposed to mechanical hemolysis during ELAD treatment due to abnormal RBC membranes, RBC membrane strength and durability, maintenance of RBC cell volume, and intermediary metabolism affecting RBC homeostasis. Anemia in the prior studies may also have been related to dilution, clotting in the catheters or dual-lumen, and stress during generation of the plasma ultrafiltrate. Additional information regarding anemia with extracorporeal procedures is provided in the [Investigator's Brochure](#).

Coagulopathy

Extracorporeal circulation increases the risk of hemorrhagic and thrombotic complications because blood is exposed to foreign non-endothelialized surfaces; cellular and acellular systems are activated/induced by exposure to foreign non-endothelialized surfaces and cause release of various intermediate products into the systemic circulation that induce hemorrhagic or thrombotic complications (Shann 2008). Patients with chronic liver disease have defective synthesis of coagulation factors (pro- and anti-coagulation factors) that can confound assessments of hemorrhagic and thrombotic complications observed in subjects undergoing ELAD treatment with or without concurrent anticoagulation. Additional information regarding coagulopathy with extracorporeal procedures is provided in the Investigator's Brochure.

Thrombocytopenia

Thrombocytopenia is a potential side effect with extracorporeal procedures; the blood and dialyzer membrane interaction can cause significant thrombocytopenia through the activation of the complement (Olafiranye 2011). Thrombocytopenia in chronic liver disease patients undergoing ELAD treatment is confounded by concurrent coagulopathy, concomitant heparin use, and ongoing hypersplenism. Additional information regarding thrombocytopenia with extracorporeal procedures is provided in the Investigator's Brochure.

Clinically-Significant Laboratory Changes While on ELAD Treatment

In general, laboratory changes in these critically-ill subjects should not be recorded as AEs. However in certain cases abnormal laboratory changes should be reported as AEs. The suggested laboratory values for hematology, serum chemistry, and urinalysis parameters that occur while the subject is on ELAD treatment that should be reported as AEs are listed in the Investigator's Brochure.

If the subject develops a laboratory abnormality meeting these criteria, a clinical diagnosis should be provided with the reported laboratory abnormality, if applicable. For example, if the subject developed hematuria in the presence of >1.0 g/dL of hemoglobin, hematuria should be listed as the clinical event and include in the details of the AE that a decrease in hemoglobin was associated with the hematuria.

If the laboratory abnormality was not associated with a clinical event, the laboratory abnormality should be listed as an AE and indicate that no clinical findings were present. For example, hyponatremia is not usually associated with any specific clinical diagnosis but is found in

subjects with clinically significant decompensated liver disease, so the specific diagnosis would not be included.

The specific notable laboratory changes for hematology, serum chemistry, and the urinalysis while on ELAD to be reported as AEs are as follows:

Hematology

- Hemoglobin >1.0 g/dL decrease from Baseline in the absence of gastrointestinal bleeding or other clinically overt sources of bleeding (e.g., hematuria, central line bleeding) or hemoglobin levels <7.0 g/dL
- WBC counts <1.5 × 10³/mL in the absence of sepsis or an uncontrolled infection
- Platelet counts <20,000 × 10³/mL and note if there is evidence of impaired clotting or clinical bleeding or oozing

Serum Chemistry

- Abrupt (within 48 hours) reduction in kidney function defined as an absolute increase in serum creatinine of 0.3 mg/dL [≥ 26.4 $\mu\text{mol/L}$ or increase of serum creatinine of 50% or more (1.5-fold) from baseline]
- Hyperglycemia (serum glucose >350 mg/dL)
- Hyperkalemia (serum potassium >7.0 mEq/L)
- Hypocalcemia (serum calcium <3.5 mmol/L)
- Hypoglycemia (serum glucose <50 mg/dL)
- Hypokalemia (serum potassium <2.0 mEq/L)
- Hypomagnesemia (serum magnesium <1.0 mEq/L)
- Hyponatremia (serum sodium <120 mEq/L)
- Hypophosphatemia (serum phosphate <0.3 mmol/L)
- Lactate >4 mmol/L

Urinalysis

- Presence of significant increase in RBCs in the urine not related to the subject's renal disease, Foley catheters, etc.
- Urine hemoglobin levels of 3+ or 4+, if not present at these levels at Baseline

Expected Adverse Reactions for ELAD Treatment

According to the literature and previous protocols using either artificial or bio-artificial liver support systems, AEs in the following five categories might be expected to be encountered during treatment.

General Risks of Fractionated Plasma Filtration

- Higher risk of bleeding due to anticoagulation and/or unfavorable effects on the coagulation system. Specifically, in liver failure subjects, where hemostasis is disturbed, the use of plasma filtration or dialysis can precipitate bleeding.
- Hypotension
- Acute transient complement activation, leukopenia, thrombocytopenia, eosinophilia
- Hemolysis due to mechanical destruction of RBCs during whole blood perfusion through the ultrafiltrate generator
- Clotting within the extracorporeal blood circuit and in the ultrafiltrate generator
- Hypersensitivity: for example, an acute reaction may be observed similar to that known as first use syndrome reaction observed in patients undergoing dialysis
- Loss of valuable substances, including proteins, hormones, nutrients, electrolytes due to either dilution or binding to components of the tubing set
- Temperature disorders (e.g. hypothermia) (Biggers 1977; Chiu 2006; VitaGen, CR-202 CSR, 2004).

General Risks Associated With Using Heparin-Based Anticoagulation

- Heparin-induced thrombocytopenia
- Bleeding due to heparin ([Hirsch 2001](#))

General Risks Associated With Using Central Venous Catheters

The general risks associated with central venous catheters may occur during insertion, while they are indwelling, and during extraction ([Kusminsky 2008](#)).

- Insertion complications (pneumothorax, malpositioning, vascular injuries, dysrhythmias, neurological complications, lymphatic complications, and guide wire loss)
- Indwelling complications (infection, thrombosis, occlusion, vascular erosion and perforation, as well as catheter fracture and embolization)
- Extraction complications (air embolism, catheter breakage or separation from hub, and catheter knotting)

General Risks Associated With Administration of Albumin

- Rash/allergic reactions
- Hypotensive episodes/shock
- Fever
- Risk of transfusion-associated infections

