9 PHARMACOVIGILANCE AND SAFETY REPORTING

An adverse event (also referred to as an adverse experience) can be any unfavorable and unintended sign (e.g., an abnormal laboratory finding), symptom, or disease temporally associated with the use of the investigational product, without any judgment about causality. An adverse event can arise from any use of the product (e.g., off-label use, use in combination with another drug) and from any route of administration, formulation, or dose, including an overdose.

It is also defined as any untoward effect, or worsening in severity, or increase in frequency of a sign, symptom, or clinically-significant laboratory abnormality, that occurs after Randomization, regardless of its relationship to the investigational product. This applies to both Control and ELAD-treated subjects.

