9.3 LABORATORY ABNORMALITIES AS ADVERSE EVENTS

Many laboratory abnormalities observed during the course of a study will be encompassed under a reported adverse event describing a clinical syndrome (e.g., elevated BUN and creatinine in the setting of an adverse event of “renal failure”). In these cases (e.g., an AE of “renal failure”), the laboratory abnormality itself (e.g., elevated creatinine) does not need to be recorded as an adverse event. Refer to the [Investigator’s Brochure](#) for hematology and serum chemistry results that occur while the subject is on ELAD treatment that should be reported as AEs (e.g., decreased platelet count or increased INR relative to baseline). However, isolated laboratory abnormalities (e.g., hyponatremia) should be reported as adverse events if they are considered to be clinically-significant by the investigator. Criteria for a “clinically-significant” laboratory abnormality are:

- A laboratory abnormality that leads to a treatment-limiting toxicity (e.g., thrombocytopenia that results in study treatment discontinuation or interruption)
- A laboratory abnormality that results in therapeutic intervention (e.g., protamine for a prolonged PTT)
- Other laboratory abnormality judged by the Investigator to be of any particular concern (e.g., detection of fibrin split products).

Significant elevations in α -fetoprotein level is an expected laboratory change in subjects on ELAD treatment. This should not be reported as an adverse event.

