8.3 ADVERSE EVENTS

The number and percent of subjects with treatment-emergent adverse events (TEAEs), TEAEs leading to ELAD discontinuation, TEAEs leading to ELAD treatment interruptions, TEAEs classified by their highest relationship to study drug, and TEAEs classified by their maximum severity, will be summarized by treatment group and by MedDRA System Organ Class and Preferred Term. Individual listings of all TESAEs, all deaths, and all TEAEs leading to ELAD discontinuation/interruption will be prepared.

Treatment-emergent adverse events are defined as those AEs with an onset date/time on or after the randomization date/time. The rationale for this is that subjects in both treatment groups are receiving standard of care at the time of Randomization. In addition summary tables of TEAEs and TESAEs will be presented based on treatment and post-treatment study periods. The study periods used in analysis for ELAD-treated subjects will be defined as Pre-ELAD (Randomization date/time to ELAD start date/time), ELAD Treatment (ELAD start date/time to Study Day 7), D8-D14 (Study Day 8 to Study Day 14) and D15-D91 (Study Day 15 to Study Day 91); and for Control subjects, Rand-D2 (Randomization date/time to Study Day 2), D3-D7 (Study Day 3 to Study Day 7), D8-D14 (Study Day 8 to Study Day 14) and D15-D91 (Study Day 15 to Study Day 91). Additional summaries of TEAEs that started between Randomization and ELAD treatment start, and TEAEs/TESAEs that started after ELAD treatment start will be presented by MedDRA System Organ Class and Preferred Term for subjects in the ELAD treatment group. For comparison purposes within these summary tables, TEAEs that started between Randomization and Study Day 2, and TEAEs/TESAEs that started after Study Day 2 will be presented for subjects in the Control treatment group.

Treatment-emergent adverse events will be coded using Medical Dictionary for Regulatory Activities (MedDRA) (Version 18.1) and incidences will be compared between treatment groups using MedDRA Preferred Terms within System Organ Classes. Subjects will only be counted once within each level of summarization.

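### Numeric laboratory AE triggers apply only while on ELAD, so the between-arm TEAE comparison can overstate laboratory-type events on ELAD

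*Protocol*

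**What the plan says.** **Rules tied to ELAD.** Protocol Appendix D has a subsection on laboratory changes during ELAD treatment. It begins "In general, laboratory changes in these critically-ill subjects should not be recorded as AEs" and then makes exceptions for suggested values "that occur while the subject is on ELAD treatment that should be reported as AEs", held in the Investigator's Brochure. It goes on: "The specific notable laboratory changes for hematology, serum chemistry, and the urinalysis while on ELAD to be reported as AEs are as follows". The list covers:

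- hemoglobin (a fall of more than 1.0 g/dL from baseline without overt bleeding, or a level below 7.0 g/dL), white cells and platelets;
- an abrupt creatinine rise (0.3 mg/dL or 50%, within 48 hours), glucose, potassium, calcium, magnesium, sodium, phosphate and lactate;
- two urinalysis findings.

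A listed abnormality with no clinical event is still entered as an AE, with a note that there were no clinical findings. Section 9.3 keeps the same scope, pointing to the Investigator's Brochure for "results that occur while the subject is on ELAD treatment that should be reported as AEs".

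**Rules for both arms.** Section 9.3 also says that isolated abnormalities "should be reported as adverse events if they are considered to be clinically-significant by the investigator". It gives three criteria: the abnormality limits treatment, it leads to an intervention ("A laboratory abnormality that results in therapeutic intervention"), or the investigator finds it of particular concern. The AE definition in Section 9 includes clinically significant laboratory abnormalities after Randomization and adds "This applies to both Control and ELAD-treated subjects".

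**Analysis.** SAP 8.3 states that "incidences will be compared between treatment groups using MedDRA Preferred Terms within System Organ Classes", and Protocol 7.6 plans the same in the Safety Population. SAP 6.2 names Fisher's exact or chi-squared tests for categorical safety variables. SAP 8.5 tabulates laboratory thresholds by arm at each visit, without inference.

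**The concern.** A between-arm comparison of AE incidence is interpretable only if the same finding has the same chance of becoming an AE in each arm. Here an ELAD subject whose hemoglobin falls by 1.2 g/dL meets a written trigger. A Control subject with the same fall becomes an AE only if someone judges it clinically significant.

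Three features sharpen this:

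- The trial is open-label. Blinded assessment begins only after discharge (Protocol 5.5.7), so the window with unequal rules is also unblinded.
- ELAD subjects alone have extra platelet and coagulation draws at hours 6-10 and 14-18 (Protocol 5.5.2).
- Protocol 9.6 treats a higher frequency on product than in controls as evidence of causality, so a reporting excess could feed into attribution.

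At stake is how the anemia, renal and metabolic terms in the TEAE tables are read. Appendix D says hemoglobin tends to fall once ELAD starts, so part of any excess may be real. The TEAE tables alone could not separate that part from reporting.

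**Working it through.** The plan states no figure on this point, so there is none to reproduce.

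**1. The rules side by side**

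| | On ELAD | Control |
|---|---|---|
| Numeric trigger list (Appendix D, 9.3) | Yes | No |
| General criteria (9.3) and AE definition (Section 9) | Yes | Yes |
| Extra platelet and coagulation draws, first 24 hours (5.5.2) | Yes | No |
| Counted in the between-arm TEAE comparison (SAP 8.3) | Yes | Yes |

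ELAD subjects have every trigger that Control has, plus the list. ELAD subjects off treatment also fall outside the list.

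**2. Where the difference can matter**

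Many triggers are extreme. Protocol 5.1.3 classes glucose below 50 mg/dL, potassium below 2.0 mEq/L, magnesium below 1.0 mEq/L, sodium below 120 mEq/L and phosphate below 0.3 mmol/L as severe abnormalities to be corrected before screening. In a Control subject such values would usually prompt treatment and so be captured by 9.3. The asymmetry is plausible mainly for the hemoglobin fall above 1.0 g/dL, the creatinine rise of 0.3 mg/dL and lactate above 4 mmol/L.

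**3. Size, under assumptions**

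Let q be the true proportion meeting a trigger, equal in both arms; e the fraction recorded on ELAD; c the fraction recorded in Control. Then spurious excess = q × (e − c).

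The documents give none of these. Assume e = 100%, q from 10% to 60% and c from 25% to 100%. Example: 0.20 × (1 − 0.50) = 0.10, that is 20% against 10%.

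Each cell shows the excess in percentage points and, in brackets, the chance of a nominally significant ELAD excess for one term. That chance comes from exact binomial enumeration with a two-sided Fisher test at 0.05 and 75 per arm (SAP 1.3).

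| q | c = 100% | c = 75% | c = 50% | c = 25% |
|---|---|---|---|---|
| 10% | 0 (1.3%) | 2.5 (4%) | 5 (13%) | 7.5 (34%) |
| 20% | 0 (1.5%) | 5 (8%) | 10 (32%) | 15 (76%) |
| 40% | 0 (1.8%) | 10 (20%) | 20 (71%) | 30 (99%) |
| 60% | 0 (1.8%) | 15 (42%) | 30 (96%) | 45 (>99%) |

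SAP 8.3 compares by Preferred Term, so q must be read per term, not as the chance of meeting any trigger on the list.

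**4. What SAP 8.5 covers**

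It tabulates, in both arms, hemoglobin below 7 g/dL, platelets, calcium, glucose, lactate, magnesium, phosphorus, potassium, creatinine change of 0.3 mg/dL or more, and sodium below 120 mEq/L. It omits the hemoglobin fall above 1.0 g/dL, low white cells and the urinalysis triggers. It works by visit, not per subject over the treatment window, and does not apply the 48-hour creatinine rule.

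**5. Thresholds that do not agree as printed**

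- Calcium: Appendix D has below 3.5 mmol/L; Protocol 5.1.3 and SAP 8.5 have 0.88 mmol/L or less. 3.5 / 0.88 = 3.98. Protocol 5.1.3 equates 0.88 mmol/L with 3.52 mg/dL, a factor of 4.0, so 3.5 mmol/L is 14.0 mg/dL. Read literally, Appendix D would widen the asymmetry.
- Platelets: Appendix D has below 20,000 × 10³/mL; SAP 8.5 has 20,000/mL or less, a factor of 1,000 apart.

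**The case against.** The strongest reply is that Control is not without a rule. The AE definition and the three criteria in 9.3 cover both arms, and Appendix D calls its values suggested, so ELAD capture need not be complete either. The Appendix D sentence that laboratory changes are generally not AEs sits under a heading about ELAD treatment, so it is not a stricter rule for Control. All of this stands. It is why the bias may be nil, and why the extreme triggers matter little.

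Second, SAP 8.5 gives an arm-neutral view from measured values. It includes mean changes relative to ELAD start, or to End of Study Day 2 for Control. For most chemistry terms that is useful evidence free of reporting differences. It is descriptive, has the gaps shown above, and leaves the TEAE tables as they are.

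Third, any bias runs against the sponsor's own product and is confined to laboratory-type terms. True, but a safety comparison should be readable in either direction.

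A reader might infer two stronger claims that the documents do not support. One is that ELAD will show an AE excess from ascertainment alone: Control capture is not known to be incomplete, and the hemoglobin fall may be a real effect. The other is that a device signal cannot be told from reporting at all: SAP 8.5 partly allows that.

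**Conclusion.** The concern holds as a risk of bias, not as a demonstrated excess. The numeric triggers are limited to time on ELAD, Control has only judgment-based criteria, and TEAE incidences are compared between arms with no sensitivity analysis for the difference. Laboratory-type TEAEs on ELAD can therefore be inflated, chiefly for the three moderate triggers.

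The size is unknown. The table runs from 0 to 45 points, but every non-zero cell rests on assumed incidence and capture rates, equal true incidence and full ELAD capture. The upper end needs a 60% incidence for a single term. The primary survival analysis is not affected. The change is worth making because it is cheap and removes a doubt that cannot be resolved from the TEAE tables afterwards.

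**What to change.** **Preferred.** State in Protocol 9.3 and Appendix D that the same laboratory AE criteria apply to Control subjects over the period SAP 8.3 already pairs with ELAD treatment: ELAD start to Study Day 7 against Control Study Days 3 to 7.

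**If conduct can no longer change.** Have the SAP derive the listed hematology and chemistry events per subject over that period, from the scheduled laboratory values in both arms (Protocol 5.5.1, Tables 2 and 3). Include the hemoglobin fall above 1.0 g/dL and low white cells, which SAP 8.5 omits. Use scheduled draws only, so that the extra ELAD platelet samples do not count.

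**In either case:**

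- Flag TEAEs raised solely by the Appendix D criteria and show the between-arm comparison with and without them in a sensitivity table. Do not drop them from the main table, since that could hide real device harm such as the hemoglobin fall.
- Leave out the urinalysis triggers, because urinalysis is not scheduled in Tables 2 and 3.
- First reconcile the calcium thresholds (Protocol 5.1.3, Appendix D, SAP 8.5) and the platelet thresholds (Appendix D, SAP 8.5).

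**Cost and limits.** A few more Control AE entries, or one derived dataset and one table. The match is not exact: ELAD may start after Study Day 3 (Table 3, note 20), and subjects discharged early need return only for Study Day 7 (Protocol 5.5.1).
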